5.1 General principles

An observed-cases approach will be used for tabulations of data by visit (that is, involving only those subjects who attended each specific visit).

Categorical observed data will be summarised using the number and percentage of subjects in each category and, if applicable, by tralokinumab naïve, re-treated, and continuously treated, and by washed-out subjects.

Continuous observed data will be summarised using the mean, SD, median, 1st quartile, 3rd quartile, minimum, and maximum values and, if applicable, by tralokinumab naïve, re-treated, and continuously treated, and by washed-out subjects.

Tralokinumab treatment naïve, re-treated, and continuously treated, and washed-out subgroups have been defined in Section 7.1.

All endpoints derived using baseline values are derived using the parent trial baseline value unless otherwise indicated.

For analyses using multiple imputation, the seed number used will be 32 and 100 MI will be carried out.

If region is used as a covariate or sub-group variable, it will be defined with the levels: North America, Europe, and Asia.

5.2 Intercurrent events

The following intercurrent events are defined to describe the treatment effect that is targeted with the different estimand strategies described underneath.

- Treatment completion: This intercurrent event occurs either when a subject completes the period of the trial the subject consented to or is withdrawn from the trial due to tralokinumab becoming commercially available in their country. This intercurrent event is introduced mainly due to the extension amendment introduced in May 2021. Notably, it was not collected in the eCRF whether a subject withdrew due to not consenting to continue in the extension of the trial. Subsequently, an algorithm was built such that withdrawals close (17 days) to the country-specific closure date were classified as treatment completers instead of as having permanently discontinued IMP. See the ADRG for a complete algorithm defining treatment completion.
- **Permanent discontinuation of IMP:** This intercurrent event occurs when a subject is withdrawn from trial while under treatment. It can occur at the subjects' own initiative, at the discretion of the investigator or the sponsor, or if the subject is lost to follow-up:
 - **Due to lack of efficacy (LoE) or adverse event (AE):** This intercurrent event occurs when it is specified that the primary reason for withdrawal from trial while under treatment is due to either LoE, or AE. Of note, the reasons "withdrawal by subject", "lost to follow-up" and "other" were queried to ensure that the underlying reason was not LoE or AE.
 - Not due to LoE nor AE: the complement to the previously specified reasons.

5.3 **Baseline presentations**

Due to safety-related analyses specified for subjects coming from the LP0162-1334 trial in the protocol, baseline presentations will be specified where applicable for subjects from the LP0162-1334 trial.

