9.5 Rescue treatment

If medically necessary (that is, to control intolerable AD symptoms), rescue treatment for AD may be provided to trial subjects at the discretion of the investigator. If possible, investigators should attempt to limit the first step of rescue therapy to topical medications, and escalate to systemic medications only for subjects who do not respond adequately after at least 14 days of topical treatment.

Subjects who receive topical rescue treatment (higher potency TCS: US class <4 or Europe class >3) will continue treatment with IMP. If TCS are used as rescue treatment, the subject should be monitored for signs of local or systemic TCS toxicity, and the safety and appropriateness of continued use should be supervised by site staff.

If a subject receives rescue treatment with systemic corticosteroids or non-steroidal systemic immunosuppressive drugs (for example, cyclosporine, methotrexate, mycophenolate mofetil, azathioprine), treatment with IMP will be immediately discontinued (see Section 10.2.3). After the treatment with these medications is completed, IMP may be resumed if deemed appropriate by the investigator, but not sooner than 5 half-lives after the last dose of systemic rescue treatment. The use of biological rescue treatment will be disallowed for the entire trial duration.

Investigators should make every attempt to conduct efficacy and safety assessments (at least disease severity scores [IGA and EASI], concomitant medications/procedures, and AEs) immediately before administering any rescue treatment. An unscheduled visit may be used for this purpose, if necessary.

Page 67 of 187

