10.2.3 Reasons for temporary discontinuation of IMP

IMP dosing MAY be temporarily suspended in the event of:

- Other intercurrent illness or major surgery.
- An infection that requires parenteral treatment with antibiotic, antifungal, antiviral, anti-parasitic, or anti-protozoal agents.

IMP dosing SHOULD be temporarily suspended in the event of:

 Treatment with systemic corticosteroids or non-steroidal immunosuppressive/immunomodulating medications (for example, cyclosporine, methotrexate, azathioprine, mycophenolate mofetil, Janus kinase inhibitors, dupilumab, or other biologics).

After the treatment with these medications is completed, IMP may be resumed if deemed appropriate by the investigator, but not sooner than 5 half-lives after the last dose of systemic rescue treatment. If any of the stopping rules are met (see Section 10.2.1) or any of the withdrawal reasons are met (Section 10.2.2), the subject must be withdrawn from the trial.

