This hypothetical assumption applied to the imputation of missing data from subjects who either completed treatment (e.g. due to commercialization of tralokinumab in their country) or permanently discontinued IMP is strong. However, assuming that these subjects continued as if they had regressed to their within-subject mean is appropriate under this hypothetical sensitivity scenario as it attempts to estimate the proportion of responders under minimal influence of survival bias.

5.6.1.1.2.2 mNRI-MI with treatment adherence MI strategy (mNRI-MI-Hyp)

This sensitivity analysis seeks to estimate a lower bound of the response by estimating the response achieved without permanent discontinuation of IMP due to LoE or AE if all subjects who withdrew for other reasons had continued in the trial like they were before they dropped out.

The response at each scheduled visit will be calculated based on both observed and multiply imputed missing or unobserved assessment data, with those having permanently discontinue IMP due to LoE or AE prior to the analysed visit imputed as non-responders. Missing assessment data will be imputed using the same 2-step MI strategy (see section 5.6.1.1.2.3) as in the hMI sensitivity analysis. Permanent discontinuations of IMP due to LoE or AE of subjects who permanently discontinued IMP for other reasons or completed the trial will be imputed using the hypothetical treatment adherence MI strategy (see section 5.6.1.1.2.3) onto subjects who either completed treatment or permanently discontinued IMP for other reasons than LoE or AE after the time they discontinue.

This hypothetical scenario sets out to estimate a lower bound of efficacy by assuming that subjects who are either observed or imputed to permanently discontinue of IMP due to LoE or AE are perpetually considered non-responders. In dealing with subjects who drop-out early, it sets a strong assumption that regression-to-the-mean can be assumed when imputing assessment data. But in doing so, this sensitivity strategy targets the same underlying target of estimation established in trials of other similar drugs in AD long-term extension trials (2) where subjects have been non-responder imputed based only on observed permanent discontinuation of IMP due to LoE or AE, with assessment data imputed using last

observation carried forward. However, last observation carried forward will not be used as it is not appropriate, see e.g., "Fallacies of Last Observation Carried Forward" (3).

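### Systemic rescue with tralokinumab suspended is not an intercurrent event in the SAP, so response seen then counts even in the analysis offered as a lower bound

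*SAP*

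**What the plan says.** SAP 5.2 states its purpose as follows: "The following intercurrent events are defined to describe the treatment effect that is targeted with the different estimand strategies described underneath". Two such events are then given. The first is "Treatment completion: This intercurrent event occurs either when a subject completes the period of the trial the subject consented to"; a subject leaving because tralokinumab has become commercially available also falls under it. The second is permanent discontinuation of IMP: "This intercurrent event occurs when a subject is withdrawn from trial while under treatment". This one is split into lack of efficacy or adverse event (LoE/AE) and all other reasons. Rescue treatment and temporary suspension of IMP appear neither there nor in the efficacy rules of SAP 5.6.

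Protocol 9.5 expects rescue. When the rescue is a systemic corticosteroid or another systemic immunosuppressant, "treatment with IMP will be immediately discontinued (see Section 10.2.3". The section it points to, 10.2.3, concerns temporary suspension: "After the treatment with these medications is completed, IMP may be resumed if deemed appropriate by the investigator". Protocol 9.5 sets the earliest time for restarting: "but not sooner than 5 half-lives after the last dose of systemic rescue treatment". Protocol 10.2.1 requires withdrawal for continuous systemic rescue of more than 3 weeks, on the investigator's assessment, from Week 16.

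The three binary analyses are in SAP 5.6.1.1. Observed cases takes scores at scheduled visits as they stand. hMI keeps observed scores and imputes the rest. mNRI-MI-Hyp does the same, but scores visits after an observed or imputed LoE/AE discontinuation as non-response. Of this last analysis the SAP says: "This sensitivity analysis seeks to estimate a lower bound of the response".

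**The concern.** The secondary objective is the efficacy of tralokinumab as continuous treatment, re-treatment or first treatment. A clear-skin score obtained on another systemic drug, with tralokinumab suspended, is weak evidence for that. Counting it is a legitimate treatment-policy choice and suits the observed-cases analysis. It fits poorly in an analysis meant to sit at the low end: the subject needed systemic rescue and is off trial drug, yet is scored as a tralokinumab responder. No planned binary analysis treats these assessments differently, so a reader cannot see how far the results depend on them.

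**Working it through.** **1. The plan's own figure.** There is none to reproduce. The SAP specifies no testing, and the protocol gives about 1,600 subjects without a formal calculation.

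**2. Following a subject through the rules.**

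| Situation | Listed event in SAP 5.2? | Score used in mNRI-MI-Hyp |
|---|---|---|
| Visit during systemic rescue of 3 weeks or less, IMP suspended | No | As observed |
| Visit during repeated short courses | No | As observed |
| Visit during rescue before Week 16 (stopping rules not yet in force) | No | As observed |
| Visit after rescue, before IMP is resumed (at least 5 half-lives of the rescue drug) | No | As observed |
| Visit during a longer course, before withdrawal | No | As observed |
| After withdrawal, coded LoE or AE | Yes | Non-response |
| After withdrawal, coded otherwise | Yes | Imputed |

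The first five rows are the gap. Observed cases and hMI also use the observed score in those rows.

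**3. Direct effect on the response rate.** Let r be the share of subjects in one of those rows at a visit, and q the share of them scored as responders. Scoring them as non-response lowers the rate by r × q. The documents give neither quantity, so both are assumptions. The last column assumes a 4-week affected window and shows what r implies: r × 52/4 courses per subject-year.

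| r | r × q for q = 25% to 75% | Implied courses per subject-year |
|---|---|---|
| 1% | 0.25 to 0.75 points | 0.13 |
| 2% | 0.5 to 1.5 points | 0.26 |
| 5% | 1.25 to 3.75 points | 0.65 |
| 10% | 2.5 to 7.5 points | 1.3 |

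For scale, the 95% Wilson half-width at n = 1,600 and 50% response is 1.96 × √(0.25/1600 + 1.96²/(4 × 1600²)) / (1 + 1.96²/1600) = 2.45 points. Multiple imputation would widen it.

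**4. Carry-over into imputation.** After Week 56, SAP 5.6.1.1.2.3 interpolates scores linearly between visits (rounding IGA) and takes the share of days in response over up to one year, not reaching back before Week 16. It uses that share as the Bernoulli probability of response. Take a subject with IGA 3 at every visit except one rescue visit at IGA 0. Interpolated IGA is below 1.5, and so rounds to 0 or 1, for just under half the visit gap on each side:

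- 8-week visits: 55 of 365 days, probability 0.15.
- 16-week visits: 111 of 365 days, probability 0.30.
- Rescue visit last before the event: 28 of 365 days = 0.08, or 56 of 365 days = 0.15.
- No rescue visit: 0.

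For EASI, assume a parent baseline of 28, so that EASI75 means a score of 7 or less. Scores of 24, 0, 24 give 33 of 365 days (0.09) with 8-week visits and 65 of 365 days (0.18) with 16-week visits. These probabilities apply in hMI, and in mNRI-MI-Hyp until any observed or imputed LoE/AE discontinuation.

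**The case against.** The strongest reply is that the phrase 'lower bound' is narrower than it looks. The same sentence ties it to response without LoE/AE discontinuation. SAP 5.6.1.1.2 gives the purpose as investigating survival bias and says the scenarios need not represent the truth. mNRI-MI-Hyp is also built to share its target with a cited earlier extension trial, where only LoE/AE discontinuation triggers non-response. A reader might infer that the scenarios were promised to bracket the true response and fail to. The SAP promises only a reasonable discussion of where it lies. What stands is that a result labelled a lower bound of efficacy will be read as one, and here it contains responses obtained off drug.

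Second, protocol 10.2.1 already removes sustained rescue from Week 16, and SAP 5.2 says other withdrawal reasons were queried for hidden LoE or AE. This stands, and it limits the gap to the rows in the table.

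Third, attribution is not clear-cut. SAP 7.1 equates 16 weeks with 5 half-lives of tralokinumab, so one half-life is 16/5 = 3.2 weeks. Three weeks after a dose, 2^(−3/3.2) = 52% of it remains. AD also fluctuates. A reader might infer that every such response was produced by the rescue drug; the documents do not show that. A low-end analysis need not prove it in order to withhold credit.

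Fourth, a reader might extend the point to higher-potency TCS rescue. The documents do not support that: IMP continues there, tralokinumab is intended for use with or without TCS, and topical use is itself an endpoint. A reader might also see a departure from the protocol. There is none on rescue: the FAS rule in protocol 14.3.5 acts only through withdrawal, so the omission is carried over.

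**Conclusion.** The point holds for systemic rescue with IMP suspended. Response seen then counts as tralokinumab response in all three binary analyses, directly and through the AUC imputation, and the one analysis presented as a lower bound does not remove it. The direction is upward relative to scoring it as non-response.

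The size cannot be determined. A reader might take one of the figures above as an estimate of overstatement; they show only how the result moves with assumed r and q, and the top row of r would need frequent rescue across the whole cohort. The effect may be small. Because the trial is descriptive and its primary endpoint is safety, no test result depends on it. It affects how the long-term response rates, and the lower bound in particular, may be described.

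**What to change.** Add 'systemic rescue treatment for AD with IMP suspension' to SAP 5.2. In mNRI-MI-Hyp, score assessments from the start of systemic rescue until IMP is resumed as non-response, and do not count those days as response in the AUC used for imputation. Report the number of subjects affected at each visit. The text should also say what applies if IMP is never resumed, and how to treat days outside the window that reach response only by interpolation from a score inside it. Leave observed cases and hMI unchanged.

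Do not extend the rule to higher-potency TCS rescue. Do not substitute the score taken before rescue either. Protocol 9.5 does ask for it ("Investigators should make every attempt to conduct efficacy and safety assessments"), but carrying it to a later visit comes close to the last-observation-carried-forward approach that the SAP rejects. No clinical rule needs to change.

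The cost is modest. Protocol 9.6 and 9.8.3 already collect medication name, indication, start and stop dates, and IMP dates. They describe no rescue flag, so rescue status must be derived. Indication is needed to separate AD rescue from systemic steroids given for other reasons, which also suspend IMP. The sensitivity estimates will be slightly lower, and mNRI-MI-Hyp will depart a little from the target of the earlier extension trial that the SAP cites.

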11.8 End of trial

An **end of treatment form** must be completed in the eCRF for all subjects completing treatment. The following data will be collected:

• Date of last administration of IMP.

An **end of trial form** must be completed in the eCRF for all subjects assigned to treatment. The following data will be collected:

- Did the subject complete the trial?
 - *If not*: primary reason for withdrawal from trial (lack of efficacy, AE, withdrawal by subject, withdrawal by parent/guardian*, lost to follow-up, death, other).
- Did the subject attend the safety follow-up visit?
 - *If not*: primary reason for not attending safety follow-up visit (lack of efficacy, AE, withdrawal by subject, withdrawal by parent/guardian*, lost to follow-up, death, other).
- Date of last contact.

^{*}For adolescent subjects as applicable.

Page 93 of 187

The end of trial form will be completed when the subject has had their last visit (see Section 7.3).

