Recovering/ resolving	The subject is clearly recovering from an event. The event is not yet completely resolved.
Not recovered/ not resolved	Event is still ongoing.
Recovered/ resolved with sequelae	The event has reached a state where no further changes are expected and the residual symptoms are assumed to persist. An example is hemiparesis after stroke.
	The stop date of the event must be recorded. In case of a SAE, the sequelae should be specified.
Fatal	The subject has died as a consequence of the event. Date of death is recorded as stop date for the AE.
Unknown	Unknown to investigator, for example subject lost to follow-up.

Note that as per the above definition, LEO Pharma uses "RECOVERED/RESOLVED" only if an event has actually stopped. According to the CDISC definition, the category "RECOVERED/RESOLVED" also includes events which have improved. However, following the LEO Pharma definitions above, such an improved event will instead be classified as "NOT RECOVERED/NOT RESOLVED" or "RECOVERING/RESOLVING".

Similarly, it should be noted that as per the above definition, LEO Pharma uses "RECOVERED/RESOLVED WITH SEQUELAE" only if an event has reached a state where the residual symptoms are assumed to persist. According to CDISC, an event is considered "WITH SEQUELAE", if it has "retained pathological conditions". Consequently, it is likely that some of the events classified by LEO Pharma with the outcome "RECOVERED/RESOLVED WITH SEQUELAE" could have been classified with the outcome "RECOVERED/RESOLVED" according to the CDISC definition.

For SAEs which have stabilised and cannot be expected to recover during study or safety follow-up periods, for example chronic or stabilised conditions, the final outcome should be kept as 'recovering/resolving' or 'not recovered/not resolved'. In addition, a statement that the SAE has stabilised or is chronic should be added to the narrative description of the SAE on the SAE form. Please note that the event should not be reported as 'recovered' on the SAE form.

Page 121 of 187

Version: 14.0

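### In mNRI-MI-Hyp, death is not itself a non-response event, so IGA 0/1 and EASI75 can be imputed after death in an analysis meant as a lower bound

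*SAP*

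**What the plan says.** The end of trial form (Protocol 11.8, and likewise 10.2.2) collects the "primary reason for withdrawal from trial (lack of efficacy, AE, withdrawal by subject, withdrawal by parent/guardian*, lost to follow-up, death, other". Death is thus a code of its own, beside AE and lack of efficacy. Under Protocol 10.2.2 a free-text specification is required only for the AE and other codes. Protocol Appendix 2 also has a fatal outcome for an AE: "The subject has died as a consequence of the event".

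SAP 5.2 defines the LoE/AE intercurrent event as the case where "the primary reason for withdrawal from trial while under treatment is due to either LoE, or AE". Every other permanent discontinuation is "the complement to the previously specified reasons". Three codes (withdrawal by subject, lost to follow-up, other) "were queried to ensure that the underlying reason was not LoE or AE". Death is not among them, and SAP 5.2 does not mention it anywhere.

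SAP 5.6.1.1.2.2 states that mNRI-MI-Hyp "seeks to estimate a lower bound of the response". Its non-response rule is that "subjects who are either observed or imputed to permanently discontinue of IMP due to LoE or AE are perpetually considered non-responders". The imputed discontinuations are placed "onto subjects who either completed treatment or permanently discontinued IMP for other reasons than LoE or AE after the time they discontinue". Remaining missing scores go through the 2-step imputation of SAP 5.6.1.1.2.3: a regression model up to Week 56, then Bernoulli draws using the subject's own past share of days in response.

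**The concern.** A bound meant to be conservative should not credit clear or almost clear skin to a subject who has died. As written, a recorded death does not stop response from being imputed at later visits, and that pushes the estimate up, against the stated aim.

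The handling also turns on a code. A fatal event recorded with AE as the primary withdrawal reason gives permanent non-response. The same event recorded as death is imputed forward as if the subject were still on treatment.

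What is at stake is limited to mNRI-MI-Hyp and its repeats in the naïve, re-treated, continuously treated and washed-out groups (SAP 5.6.1.1.3). The main efficacy analysis uses observed cases (SAP 5.6.1.1.1), the primary endpoint is the number of AEs (SAP 5.5), and no testing is specified (SAP 2).

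**Working it through.** The plan gives no figure to reproduce on this point, so the check has two parts: tracing the code through the definitions, and bounding the size.

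**Tracing the code death**

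1. It is neither LoE nor AE on the form, so the recorded reason does not meet the LoE/AE definition.
2. It is not one of the three queried codes, so the SAP describes no step that would move it to LoE/AE.
3. Reading A: it is a permanent discontinuation in the complement. Scores after death are imputed by the 2-step method. The subject is also eligible for an imputed LoE/AE discontinuation and is a non-responder after it, if one is drawn.
4. Reading B: it is no defined intercurrent event, because the SAP 5.2 description of how discontinuation arises (subject, investigator or sponsor decision, or loss to follow-up) omits death. The SAP then gives no rule. The Bernoulli draws are specified for the time after an intercurrent event, so they are not clearly specified for this subject either.
5. On both readings the death itself does not trigger non-response. Reading A is the more natural one.

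**Size, on reading A**

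Inputs:
- N = 1,600, the approximate trial size in Protocol 14.1. The EASI75 denominator is somewhat smaller, because EASI75 is not applicable to subjects from TRA-WEI-0015-I.
- D = subjects coded death before the visit. Not in the documents; assumed 1 to 20.
- p = imputed response share for these subjects. Not in the documents; assumed 0.3 to 0.8.
- q = chance that an LoE/AE discontinuation has been imputed by that visit. Not in the documents; 0 gives the largest shift, and 0.3 is shown for comparison.

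Overstatement at a visit = (D/N) × p × (1 − q).

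- D = 1, p = 0.3, q = 0: 1/1,600 × 0.3 = 0.00019, or 0.019 percentage points (pp).
- D = 20, p = 0.8, q = 0: 20/1,600 × 0.8 = 0.0100, or 1.0 pp.

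| D | q = 0, p = 0.3 to 0.8 | q = 0.3, p = 0.3 to 0.8 |
|---|---|---|
| 1 | 0.019 to 0.050 pp | 0.013 to 0.035 pp |
| 5 | 0.094 to 0.250 pp | 0.066 to 0.175 pp |
| 10 | 0.188 to 0.500 pp | 0.131 to 0.350 pp |
| 20 | 0.375 to 1.000 pp | 0.263 to 0.700 pp |

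For comparison, the complete-data Wilson 95% half-width is z/(1 + z²/n) × √(r(1 − r)/n + z²/(4n²)), with z = 1.96 and response rate r. At n = 1,600 it is 2.45 pp for r = 0.50 and 2.33 pp for r = 0.65.

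Subgroup sizes are not given. For an assumed 100 to 400 subjects, one such death moves the rate by between 1/400 × 0.3 = 0.075 pp and 1/100 × 0.8 = 0.8 pp. The Wilson half-widths for r = 0.50 to 0.65 are 4.65 to 4.88 pp at n = 400 and 9.19 to 9.62 pp at n = 100.

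**The case against.** The strongest reply is that the imputation fits the declared target. SAP 5.6.1.1.2 calls its scenarios hypothetical, and SAP 5.6.1.1.2.2 asks what would have happened had those who left for reasons other than LoE or AE carried on. On that view, making death a non-response swaps a hypothetical strategy for a composite one, counts a death unrelated to drug or disease as an efficacy failure, and moves away from the comparator-trial definition the SAP cites. It is true that this is a choice between strategies and that the departure has to be declared. It does not remove the gap: hMI already covers the scenario in which everyone continues, and continued response after death is not a meaningful target for the analysis offered as the lower bound.

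A second reply concerns the protocol. Its section 14.3.5 regarded withdrawn subjects as non-responders, but that sentence follows one about the stopping rules, and SAP Panel 5 openly replaces the method. Whether the protocol meant to cover deaths is an inference, so the point does not rest on it.

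A third reply is that the ADRG may contain a rule. It is not among the documents. The SAP cites it for the treatment-completion algorithm and for vital-sign and laboratory criteria, not for death. That algorithm classes withdrawals within 17 days of country closure as completers; a death caught by it would also be imputed forward.

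Four stronger readings are tempting and are not supported:

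- That non-response is set solely from the recorded reason. The SAP also sets it after an imputed LoE/AE discontinuation, which a subject coded death can draw.
- That the SAP expressly imputes response after death. On reading B it is silent.
- That sites did split fatal events between the two codes. The form permits it; nothing shows it happened.
- That counting deaths in the treatment-adherence model would add a calculable number of failures among living subjects. SAP 5.6.1.1.2.3 does not state which discontinuations are events and which are censored, so no figure can be derived.

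**Conclusion.** The point stands as a minor gap in the definition of the intercurrent events. In mNRI-MI-Hyp a death coded as such does not make a subject a non-responder. On the natural reading, later response is imputed until an LoE/AE discontinuation is drawn, if one ever is; on the other reading there is no rule. Either way the handling works against the lower-bound aim and differs from that of a fatal event coded AE.

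The overstatement is at most about 0.02 to 1.0 pp per visit. This rests on assumed values of D and p, the approximate N of 1,600 and q = 0. The upper end needs 20 deaths coded death with a response share of 0.8, and is still under half the complete-data Wilson half-width. Intervals under multiple imputation would normally be wider. Conclusions from the main efficacy analysis and the primary endpoint do not change.

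**What to change.** In SAP 5.2, name death as an intercurrent event. In SAP 5.6.1.1.2.2, state that all scheduled visits after an observed death are non-response in mNRI-MI-Hyp, whatever the withdrawal code. Add that this rule does not by itself make deaths LoE/AE events in the treatment-adherence model, so that it does not alter what is imputed for living subjects.

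The cost is a sentence or two of text and one programming condition on a code already collected. The downside is a slightly lower estimate and a small departure from the comparator-trial definition, which the SAP describes as non-response only on observed LoE/AE discontinuation. The departure should be stated where that comparison is made.
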